10.0 Procedures Involved

10.1 *Provide a description of **all research procedures or activities** being performed and when they are performed once a subject is screened and determined to be eligible. Provide as much detail as possible.*

NOTE: This should serve as a blueprint for your study and include enough detail so that another investigator could pick up your protocol and replicate the research. For studies that have multiple or complex visits or procedures, consider the addition of a schedule of events table in in your response.

Response:

Pilot Phase: If families meet the criteria gathered from the initial screen, research staff will review the details of the study procedures, and the parent/legal guardian of each child will be asked to review and sign consent forms as described herein. After consent procedures, children will be asked to taste test up to 5 main dishes (e.g. turkey sandwich, peanut butter and banana sandwich) and up to 5 sides (e.g. applesauce, carrot sticks, mandarin oranges). A visual face scale with 3-points (4-5 year-olds) or 5-points (6-8 year-olds) will then be used to aid children in rating their liking and rank-ordered preference for presented options (see attached Data Collection Form Pilot Phase and Script Pilot Phase documents). While children are completing the taste tests, participating parents will be asked to complete a brief demographic survey using either an electronic tablet or pen and paper (see attached Pilot Parent Demographic Survey Questions). After data collection is complete, families will receive \$10 in cash to thank them for participating and children will receive a small prize like a sticker.

Experimental Phase: The experimental phase will be a cluster-randomized trial. Six locations of Anderson's will be paired based on income levels in the surrounding census tracts. A location from each pair will be randomized to each study group (intervention, control). Phased data collection will occur, with each pair of restaurants assigned to a cohort (see Figure 1 below). Within-restaurant measures will be collected using electronic devices (or with paper/pen if that is preferred by the participant during in-person data collection).

Recruitment Period (about 3-4 months per cohort). Families entering study restaurants during the recruitment period will be informed about the study opportunity and recruited into the study if interested and eligible. Consent forms will be completed electronically or on paper by parents granting permission for their child's participation as well as their own. These will also be signed by the study staff member obtaining consent. The original will be kept by the study personnel, and a copy will be given to the participants for their records. Hard copies obtained by study personnel will be kept in a locked cabinet separate from any participant data; electronic copies will be stored on a secure server separate from/not linked with participant data. Study staff will also administer assent procedures to children.

For those recruited remotely, procedures will generally be the same except potential participants entering the restaurant during the recruitment period will view written information about the study in the restaurant (e.g., on signs, table tents) rather than being informed by study staff directly. Potentially interested participants can contact study staff to receive a website link to access a screening questionnaire. Consent forms will be completed electronically by parents. For those who participate remotely, the parent only has to grant permission for their own participation, and not the child's, given that we are not including any child surveys for participants recruited remotely. In other words, for any families participating remotely, data will be collected from the parent only (see measures for more information on specific measures, as well as the attachments). Electronic copies of participant's screening and consent information will be stored on a secure server separate from/not linked with participants' study data.

After in-person recruitment, families will be asked to order and eat like they normally would and to alert study staff after they finish eating for their initial assessment, during which study staff will administer baseline study measures as described below assessing orders, intake, and demographics. Those participating in remote data collection can complete screening and consent procedures at any point in their study visit and then will be provided with a link to complete baseline measures via an online survey assessing orders and demographics, completed by the parent. There is no child survey or baseline intake assessment in remote cohorts. Parents who contact the study team but do not immediately take the survey will be sent a follow-up text about 24 hours later to see if they are still interested in participating (see recruitment scripts).

After baseline data collection, families will receive study materials in-person or via postal mail, including their debit card for study payment and related instructions, as well as intervention materials (see Sample Marketing Materials; Minor changes may be made to these for each cohort (e.g., to reflect the correct dates each year). If any changes greater than these minor changes are to be made, we will resubmit the materials to the IRB). Intervention materials include placemats – either placemats promoting special healthier featured kids' meals (intervention group; see attached Sample Marketing Materials_Menu) or generic placemats depicting the restaurant's entire children's menu (control group; Sample Marketing Materials_Menu). Intervention placemats will also promote the

upcoming opportunity for children to redeem the token that comes with all kids' meals at this restaurant for a toy instead of a dessert. Families recruited into the study will also receive paper or electronic frequent diner cards (see attached Sample Marketing Materials_Punch Card). In the intervention group, participating children must order a featured healthier meal 6 times during the exposure period to earn a free kids' meal. Information about the two featured meals will appear on the cards. Restaurant staff will validate the cards when a target meal is purchased and the card is presented (e.g., by marking an image of the meal using a novelty stamp when that meal is purchased and a paper card is presented or by scanning the image when an electronic frequent diner card is presented). Control group cards will be similar but can be used during purchases of any kids' meal. When either card is marked, the child will also receive a small prize (e.g., sticker). Restaurant staff will be trained to know which items come with the two featured meals, to allow use of the intervention group's healthy frequent diner cards only for purchases of those meals, and to only allow one purchase per card per visit.

Exposure Period (about 2 months per cohort). Participating families will return to the Anderson's location where they were recruited on a weekly basis during an exposure period lasting about 2 months (they will be asked to visit at least 6 times during this period). Placemats will be available at the restaurant entrance, and signage with corresponding information will be displayed. In intervention restaurants, the placemats and signs will advertise promoted meals and the opportunity for children to redeem their "dessert" token for a toy. In intervention restaurants, boxes of small assorted toys (e.g., yo-yo, action figure, mini puzzle) will be available. This opportunity will not be advertised in control restaurants, but we will offer to provide them with toys in case a customer should request one.

Participating children will be able to use their frequent diner card during this time to earn a free meal during the subsequent redemption period. Families will also be asked to complete a brief (<20 min) online survey (described below; see attachment Midpoint Online Parent Survey Questions) once per week to monitor restaurant patronage. During at least one cohort of in-person data collection, one of the midpoint assessments will also feature remote food photography (see measures), to train and prepare the participants to provide dietary intake data via remote food photography at post-test during this/these cohort(s). During at least one cohort of in-person data collection, study staff will also conduct observations of parents and children in the restaurant during this time period, within a subsample of participating families as described below (see attachments; Observation Data Collection Form and Dyadic Parent-Child Interaction Coding System (DPICS) Form).

Redemption Period & Post Assessment (about 3 months per cohort). Study staff will be in the restaurant throughout this period, and entering families will identify themselves to study staff using their electronic or paper frequent diner cards. Study staff will photograph or collect (if paper) or confirm the presence and status of the cards (if electronic) and ask families to order and eat like they normally would and to not throw out any food or leftovers. Families will be able to redeem

any earned free kids' meals during this time. When the family is done eating, they will take a photograph of the child's food using remote food photography methods, which involves using their electronic device (e.g., cell phone or iPad), if they are participating in a cohort in which this measure is being implemented. For all families, study staff will then approach the table to administer study measures as described below assessing orders, perspectives on the meal, and intake. Two days later, families will also be prompted to complete an online dietary recall (ASA24) about the child's dietary intake the day after their post assessment. Study materials (placemats and signs) will remain in the restaurants during the redemption/post period.

Families redeeming frequent diner cards as a part of the remote data collection will first send images of the completed diner card with ID numbers to study staff. Staff will then ask families to order and eat like they normally would and to not throw out any food or leftovers. When the family is done eating, they will alert study staff via phone, text, or email and be sent links to complete an online survey on which parents report on orders as well as take a photograph using remote food photography methods, which involves using their electronic device (e.g., cell phone or iPad), to capture the child's dietary intake at post-test (see attached mid-point Remote Food Photography one-sheet). As mentioned above, child-report survey data will not be collected for remote cohorts. These families will also be prompted to complete the online dietary recall (ASA24) about the child's dietary intake the day after their post assessment.

Compensation. Participating families can receive up to \$300 for participating in the study (\$265 for all standard assessments; plus an additional \$35 if in the observed subsample). Families will receive up to \$50 for completing measures at the initial time point. Then, throughout the exposure period (midpoint), they can receive up to \$120: \$90 of the \$120 will be provided during the exposure period for completion of weekly online surveys (divided up and paid weekly), and an additional payment will be provided later for each of the weekly exposures indicated on their frequent diner card ($\$5 \times \text{number of exposures}$, max = 6; determined upon collection of the card at post-test). After the midpoint assessments, families will receive one more payment; this payment will be administered following post-test and will include up to \$50 for completion of in-restaurant post-test measures (final survey; intake measures used during their cohort – i.e., weighed plate waste and/or remote food photography), plus a \$20 bonus for following post-test procedures as instructed (i.e., turning in their frequent diner card at post-test if paper version; coming to originally-scheduled appointment time if in-person), \$25 for completion of the online dietary intake survey (ASA24), and the aforementioned midpoint payments from frequent diner card use. Families will also receive their free kids' meal at post-test if frequent diner cards are completed, and those randomly selected to be included in the observed subsample will receive an additional \$35. Children will receive a small prize (e.g., stickers) each time their frequent diner card is used. Payments will be made via a prepaid debit card provided by the study.

[figure not shown]

Figure 1. Data collection timeline for an individual cohort with main measures. These procedures will happen repeatedly over about 3-4 years to collect data from about 3-5 cohorts.

10.2 Describe what data will be collected.

NOTE: For studies with multiple data collection points or long-term follow up, consider the addition of a schedule or table in your response.

Response: Data collected are detailed below. In addition, please see attachments for corresponding forms/surveys with specific questions to be administered.

Pilot Phase: We will collect data on children’s liking of and preferences for the foods they taste during taste tests, as well as parent-reported demographics.

Experimental Phase: Orders. At initial and post-assessment time points, researchers will ask the participating parent to identify all items ordered for and eaten by the child that day and will record: 1) whether or not one of the healthier featured kids’ meals was ordered, and 2) the specific main dish(es), side dish(es), beverage(s), and dessert(s) ordered for/ eaten by the child, noting whether each item was shared, taken to go, or was finished in the restaurant. Total calories, saturated fat, sugar, and sodium ordered for the child will be calculated using nutrition information available from the restaurant. At post-test, families’ frequent diner cards will also be photographed or collected (if paper version) or confirmed via our electronic records (if electronic version). Researchers will record the number of marks/punches on the card, and in the intervention group, which of the healthy meals the marks correspond to. Questions about orders will also be asked via online survey at midpoints (see attachments). For those participating in the remote data collection, orders will be collected at all of these same time points via online surveys sent to participants’ electronic devices.

Sales Data. We will collect aggregated sales data from the restaurant to monitor sales of kids’ meals across all patrons in Anderson’s restaurants during the recruitment, exposure, and redemption periods and parallel time points one year prior. These data are aggregated and de-identified and do not require IRB approval; therefore, the sales data are not described further herein.

Dietary Intake at the Restaurant. Children’s dietary intake will be measured using plate waste methodology, a gold standard for measuring dietary intake. Study staff will ask the parent which items were ordered for and consumed by the target child, recording the names of the items, and will collect all uneaten food and

containers from the child's meal, sealing them in plastic bags labeled with the child's ID and the item name. Items will be post-weighed in the laboratory following data collection using a digital scale. Pre-weights will be measured by purchasing 3 replicates of each food/beverage item ordered and averaging their weights to arrive at a standard pre-weight. Grams consumed will be converted to percentages using total grams from pre-weights, and these percentages will be multiplied by the total calories, saturated fat, sodium, and sugar found in the full item to calculate calories and nutrients consumed.

Children's dietary intake will also be measured using Remote Food Photography methodology during at least one cohort of in-person data collection during the post assessment, with the opportunity to practice this at one of the midpoint visits. This will be the only measure of dietary intake in participants participating remotely, since weighted plate waste is not possible in those instances. For the Remote Food Photography assessment the parent will take a photograph (approximately 24 inches from the meal using a 45-degree angle) of the child's meal before it is eaten and a second photograph of any uneaten food following procedures outlined in the remote food photography guide and the training video (mid-point Remote Food Photography training video script attached). Photographs will be checked by study staff for proper data capture. Amount consumed will be estimated as percentages using pre-weights and photographs of menu items.

Parents will also be prompted to follow these procedures at one of the weekly midpoint assessments during at least one cohort of in-person data collection as a way to practice and receive feedback on the process prior to the main post-test dietary intake assessment. Parents will receive detailed instructions and watch a short instructional video (see mid-point Remote Food Photography training video script and mid-point Remote Food Photography one-sheet attachments) explaining how to take proper photographs of their child's meal. Parents will then practice the remote food photography method on their child's meal, sending the photographs to study staff to check for clarity and completeness of data. Dietary intake will not be assessed at the initial/baseline time point for remote cohorts to streamline the initial assessment in the absence of in-person support.

Total Daily Dietary Intake. Parents will report children's daily dietary intake using the Automated Self-administered 24-hour Dietary Assessment Tool (ASA24; <https://asa24.nci.nih.gov/>) at post-test (focusing on the day after the post-test restaurant visit).

Parent Perspectives & Demographics. Using an electronic device, parents will complete survey questions. At the initial assessment these will include demographics (e.g. parent age, sex, race/ethnicity, education level, income, target child age, sex, race/ethnicity, height, weight). At initial/baseline and post-test assessments parents will indicate who selected the child's meal, the reason for the meal choice, and how often the child eats at restaurants in general and this specific restaurant. At post-test, parents will also report on their child's visits to locations of the study restaurant since our last contact with them and perspectives on the intervention components (placemats, frequent diner cards).

Parent Mid-Point Surveys. In an online survey parents will answer questions about their visits to locations of the study restaurant since last contact and child meal selection. They will also be asked about visits to restaurants in general, parent meal selections, parent and child liking of the meals, and general parenting practices. Parents will also complete remote food photography during one of the midpoint assessments as described above.

Child Perspectives. At initial/baseline and post-test assessments, study staff will interview the participating child, entering answers into an electronic tablet. Child questions will include: whether the child knew what s/he would have before arriving at the restaurant; whether s/he had been to this restaurant before; whether this was the meal s/he typically ordered; who selected the meal; and how it tasted. At post children will also answer questions about the intervention components. The child will not be interviewed (i.e. there will be no child-report survey) for remote cohorts.

Observations of Family Interactions. Parent-child interactions will be unobtrusively observed in a random subsample during the exposure period. Two study staff members will be at a table in the restaurant to unobtrusively observe parent-child interactions, for a total of about 10 minutes (about 5 minutes before the meal and about 5 minutes during the meal; see attachments Observation Data Collection Form, modified from those previously used by [name] and colleagues, and Dyadic Parent-Child Interaction Coding System (DPICS) Form). This portion of the study will be conducted with a subsample of participants during select, in-person cohorts. It will not be completed (i.e. there will be no observations of family interactions) for remote cohorts. Following the brief in-restaurant observation, families in the observed subsample will complete a brief online survey (see attachment: 2023 Observation Parenting Survey). The survey will include a few questions about their experience in the restaurant during the observation as well as a few questions about parenting that used to be part of the Midpoint 1 survey, which was reduced slightly as communicated in prior modifications.

Implementation. At the conclusion of each cohort's data collection period, tracking of intervention components will occur (e.g. number of placemats and toys distributed). In addition, we will monitor implementation during the exposure and post periods (e.g., are study materials displayed as specified). This is not a human subjects research component and therefore it is not discussed further herein.

Table 1. Study outcomes by time point and measure

	Initial Assessment	Midpoint Assessment	Post Assessment
Orders (Primary outcomes)			
Items ordered for children in study sample and their parents	P	P/F	P
Total calories, saturated fat, sodium, and sugar in children's orders	P/N	P/F/N	P/N
Children's meal orders in study restaurants overall during study period	S*	S*	S*
Children's consumption (Secondary outcomes)			
Total calories, saturated fat, sodium, sugar consumed in restaurant	W^N		W/N
Total daily calories, saturated fat, sodium, and sugar consumed			P (recalls)

Other Variables of Interest			
Demographics	P		
Parent perspectives on restaurant/study experience	P	P	P
Child perspectives on restaurant/study experience	C^	P	C^
Observations of family interactions		O**	
Other implementation measures (e.g., tracking placemats)			O***

P: parent report; F: frequent diner cards; N: nutrition information from restaurant; S: sales data; W: plate waste or food photography (remote cohort only); C: child report; O: observation. Shaded bars depict individual measures. *Collected throughout/ from 1 year prior to study start. **Random subsample. ***Collected after each post period. ^Not collected for remote cohort.

10.3 List any instruments or measurement tools used to collect data (e.g. questionnaire, interview guide, validated instrument, data collection form).

Include copies of these documents with your submission.

Response:

Pilot phase:

- Script Pilot Phase
- Data Collection Form 4-5 year-olds (Pilot Phase)
- Data Collection Form 6-8 year-olds (Pilot Phase)
- Pilot Parent Demographic Survey Questions

Experimental phase:

All in-person participants

- Initial Visit Script (Experimental Phase)
- Initial Visit Parent Survey Questions (Experimental Phase)
- Initial Visit Parent Survey Questions QR Version (for parents who wish to leave the restaurant early without completing the interview) – (Experimental Phase)
- Initial Visit Child Survey Questions (Experimental Phase)
- Plate Waste Form (Experimental Phase)
- Post Assessment Script (Experimental Phase)
- Post Assessment Parent Survey Questions (Experimental Phase)
- Post Assessment Child Survey Questions (Experimental Phase)

Remote cohorts only

- Consent, Screening & Initial Visit Parent Survey Questions (Experimental Phase) [REMOTE]
- Recruitment Script (Experimental Phase) [REMOTE]
- Post Assessment Script (Experimental Phase) [REMOTE]
- Post Assessment Parent Survey Questions (Experimental Phase) [REMOTE]
- Reminder Call Email Script (Experimental Phase) REMOTE

Both in-person and remote cohorts:

- Mid-Point Online Parent Survey Questions

Select participants/cohorts:

- Mid-Point RFPM Training Video Script
- Mid-Point RFPM Participant Training One-Sheet
- Post Assessment Remote Food Photography Methodology (RFPM) Form (Experimental Phase)
- Family/ Server Observation Data Collection Forms

10.4 Describe any source records that will be used to collect data about subjects (e.g. school records, electronic medical records).

Response:

N/A, no source records will be used to collect data about subjects.

*10.5 Indicate whether or not **individual** subject results, such as results of investigational diagnostic tests, genetic tests, or incidental findings will be shared with subjects or others (e.g., the subject's primary care physician) and if so, describe how these will be shared.*

Response:

N/A, no individual subject results will be shared with subjects or others.

*10.6 Indicate whether or not **study** results will be shared with subjects or others, and if so, describe how these will be shared.*

Response:

No, study results will not be shared with subjects or others besides publication of study results in scientific journals and accompanying write-ups (e.g., conference presentations, press releases to promote published articles). All such publications will feature data in aggregate and no identifying information.

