4.0 Study Design

4.1 Describe and explain the study design (e.g. case-control, cross-sectional, ethnographic, experimental, interventional, longitudinal, observational).

Response:

Pilot Phase: A cross-sectional study design will be used. About 25 children from 1-3 restaurant locations will participate in taste tests to inform food selections for the subsequent experimental phase. Families will be asked if they want to

participate in taste tests during a regular visit to a location of the study restaurant (Anderson's Frozen Custard). Participating children will taste up to 5 side dishes (e.g. applesauce, carrot sticks, mandarin oranges) and up to 5 main dishes (e.g. turkey sandwich, peanut butter and banana sandwich). They will then use a visual face scale to rate their liking and rank ordered preferences for presented options and be asked for their opinions on the foods (e.g., why they liked/disliked the food items). Parents will be asked to complete a brief demographic survey on an electronic tablet or with pen and paper.

Experimental Phase: A cluster-randomized design will be used. 6 locations of Anderson's, a regional quick-service restaurant in the Buffalo, New York, area will be paired based on income levels in the surrounding census tracts. A location from each pair will be randomized to each study group (intervention, control). Recruitment and data collection will be conducted across about 3 to 5 cohorts, with recruitment conducted either in person or remotely during a family's regular visit to Anderson's.

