6.0 Inclusion and Exclusion Criteria

6.1 Describe the criteria that define who will be **included** in your final study sample.

NOTE: This may be done in bullet point fashion.

Response:

Eligibility criteria for both phases include: English-speaking parent/guardian at least 18 years old; an English-speaking child who is 4-8 years old at the time of recruitment (child may turn 9 years old during the study time period); and the child must eat food from restaurants at least 2-3 times each month. In addition, during the experimental phase, they must be eating a meal at one of the Anderson's locations specific to that cohort on the day they are recruited (i.e. day of baseline data collection). We will also ensure that the child does not have allergies that would preclude their safe participation in the study. These criteria were selected with the goals of results being generalizable to children who eat in these settings regularly and demographics of the geographic area in which we plan to conduct the study.

6.2 Describe the criteria that define who will be **excluded** from your final study sample.

NOTE: This may be done in bullet point fashion.

Response:

We will exclude anyone who:

- Is under 18 years of age (parent/legal guardian)
- Does not have a child in the range of 4-8 years at the time of recruitment
- Does not speak English fluently (both parent and child)
- Does not eat food from a restaurant at least 2 – 3 times per month (child)
- Is not eating a meal at one of the Anderson's locations specific to the cohort on the day recruited (child; experimental phase only)
- Has food allergies that preclude safe participation in the study (child)

For participants recruited remotely, we will exclude anyone who:

- Does not have regular internet access.

6.3 Indicate specifically whether you will include any of the following special populations in your study using the checkboxes below.

NOTE: Members of special populations may not be targeted for enrollment in your study unless you indicate this in your inclusion criteria.

Response:

- ☐ Adults unable to consent
- ☒ Individuals who are not yet adults (infants, children, teenagers)
- ☐ Pregnant women
- ☐ Prisoners

6.4 *Indicate whether you will include non-English speaking individuals in your study. **Provide justification if you will exclude non-English speaking individuals.***

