11.0 Study Timelines

11.1 Describe the anticipated duration needed to enroll all study subjects.

Response:

We anticipate it will take about 5 years to enroll all study subjects, with enrollment of each cohort taking about 3-4 months.

11.2 Describe the duration of an individual subject's participation in the study. Include length of study visits, and overall study follow-up time.

Response:

Pilot Phase: Children will participate individually in one in-restaurant taste test session for up to 30 minutes.

Experimental Phase: Families will be recruited and enrolled during the recruitment & initial assessment period which will occur across a span of about 3-4 months per cohort. In the subsequent exposure period (a predetermined period of about 2 months to follow recruitment), families will return 6 times to the restaurant they were recruited in for a meal and will complete a brief online survey (<20 min). After this, families will return once during a predetermined period of up to 3 months for a final meal and assessment. Families will also be prompted to complete an online survey about their child's dietary intake the day after the last session. Across study periods, each family will participate for about 6 months total. The total duration of participation is the same for families recruited remotely, with minor differences in specific procedures as described herein.

11.3 Describe the estimated duration for the investigators to complete this study (i.e. all data is collected and all analyses have been completed).

Response:

We estimate it will take about 6 years to complete this study.

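### Restaurant arms appear to be known while families are still being approached and screened, and nothing in the protocol keeps recruiting staff unaware of them

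*Combined protocol and SAP*

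**What the plan says.** Sections 4.1 and 10.1 randomise restaurants, not families: six locations form three income-matched pairs, and one location of each pair goes to each arm. Neither section dates the randomisation. Section 10.1 describes phased data collection "with each pair of restaurants assigned to a cohort".

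Recruitment then runs for about 3-4 months per cohort (section 10.1, Recruitment Period): "Families entering study restaurants during the recruitment period will be informed about the study opportunity and recruited into the study if interested and eligible". In person, staff approach families who seem to have a child of the right age and are trained to determine eligibility from the answers (section 26.2). They put the screening questions aloud (section 8.1).

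On materials, section 10.1 says: "After baseline data collection, families will receive study materials in-person or via postal mail". The package holds the study debit card, the placemat and the diner card. The last two differ by arm. In the intervention group, "participating children must order a featured healthier meal 6 times during the exposure period to earn a free kids' meal"; the control card accepts any kids' meal. Section 4.1 places the handing out of intervention placemats after baseline within the recruitment/initial period, to families in what it already calls intervention restaurants.

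The exposure period is "a predetermined period of about 2 months to follow recruitment" (section 11.2).

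**The concern.** In a cluster-randomised trial, randomising the clusters does not by itself balance the people in them. If families are selected after the arm is known to those selecting them, the arms can come to hold different kinds of families before any intervention starts. Here the relevant traits would be interest in healthier food and usual ordering habits, which bear directly on the outcomes. With three restaurants per arm, a tendency that runs the same way in every pair would not average out. The random effect for restaurant would not remove it either, because it would be aligned with study group.

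**Working it through.** No figure in the protocol bears on this point. The check is of the order of events, who can know the arm, and what the analysis would do about an imbalance.

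**1. Is the arm known during recruitment?** It is implied, not stated. Arm-specific materials go to each family after its own baseline (section 10.1), within the recruitment/initial period (section 4.1). They cannot be given out unless the arm has been set. Recruitment lasts about 3-4 months, so early families can receive theirs while later ones are still being approached.

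**2. Can recruiters know it?** In-person delivery is allowed. The protocol does not say who hands the materials over; I assume the study staff in the restaurant, who also recruit. No section keeps recruiters or screeners unaware of the arm.

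**3. Is there room for judgement?** In person, yes: staff decide which families to approach and determine eligibility after a spoken screen (sections 8.1, 26.2). In remote cohorts there is less room. Families respond to signs, table tents or social media, and an online form determines eligibility (sections 8.1, 9.3, 26.2).

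**4. Would the analysis remove an imbalance?**
- The Aim 1 model (section 17.1) has group, time, their interaction and a random restaurant effect, with a contrast on the group difference at post. That contrast does not subtract the initial difference.
- For Aim 2, remote cohorts have no baseline intake (sections 10.1, 10.2), so an intake imbalance there could not be seen.
- Propensity scores come in only if demographic differences are substantial (section 17.1). No threshold is given, and demographics need not capture food preference.

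**5. Scale, on assumed values only.** Let D be the between-arm difference in the share of families inclined towards featured meals, and R how much more often such families order them. The spurious difference in orders is D x R.

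| D (assumed) | R = 10 points | R = 21.1 points |
|---|---|---|
| 5 points | 0.5 | 1.1 |
| 10 points | 1.0 | 2.1 |
| 20 points | 2.0 | 4.2 |

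The planned difference is 27.8% - 6.7% = 21.1 points (section 17.2). D and R are not in the documents, so the table shows how the bias scales and does not estimate it.

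**6. Is early disclosure needed?** No. Exposure follows recruitment (section 11.2), and the cards earn credit only in the exposure period. Postal delivery is already allowed.

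**The case against.** The strongest case on the other side is that this is a reporting gap. Much of it stands:

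- The invitation is already neutral and common to both arms: a study of what children like to eat in restaurants, with the same visits and a free kids' meal to earn (sections 9.1, 9.3). A reader might infer that families choose to join on the basis of different offers. The documents do not support this: the materials come after consent and baseline, so a family's own placemat and card cannot affect its decision or its baseline order. The scripts and consent forms are not in the supplied text.
- A reader might infer that cards held by early families contaminate later families' baselines. No route is described. Entrance placemats and signs belong to the exposure and redemption/post periods.
- A reader might infer that the allergy criterion works differently by arm, because only one card requires featured meals. Section 6.1 has one sentence for everyone, "We will also ensure that the child does not have allergies that would preclude their safe participation in the study", and names no arm or food. Hypothesis 1c compares featured-meal sales in both sets of restaurants, so those meals appear to be on sale in both. Arm-specific use is conjecture.
- A reader might put the bias in calories, using the 556.6 - 473.3 = 83.3 kcal gap in section 17.2. Shifting the share of health-minded families by an assumed 10 to 25 points gives 8.3 to 20.8 kcal, seemingly as large as the 0.211 x 83.3 = 17.6 kcal implied through entree choice. But that gap separates children by the entree they ordered, not by type of family. Diluting both sides equally gives 0.10 x 0.211 x 83.3 = 1.8 to 0.25 x 0.211 x 83.3 = 4.4 kcal. None of these is an estimate, because the shift is invented.
- Most eligibility criteria are factual, the pairs are income-matched, and initial orders are collected in all cohorts.

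These points narrow the concern but do not close it. Neutral wording does not control whom staff approach, and income matching of neighbourhoods does not control which families within a restaurant are enrolled.

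**Conclusion.** The concern holds in limited form. The protocol leaves open a route for selection by staff who know the arm, chiefly in in-person cohorts, and neither the contrast at post nor the conditional propensity scores close it. This rests on two readings: that allocation precedes or overlaps recruitment, which the handing out of materials implies, and that the staff who recruit can learn the arm. Direction and size are unknown, and no calorie figure should be attached. It does not follow that the arms will differ, that families are offered different things at consent, or that allergy screening differs by arm. The change is worth making because it removes a bias route without altering sample size or visits.

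**What to change.** - State when each pair is randomised. Draw its allocation, or at least disclose it to recruiting staff, only after the last baseline of that cohort.
- At enrolment give only the debit card. Send the placemat and diner card by post or electronically just before exposure begins.
- Provide for reused pairs. Section 4.1 says "Recruitment and data collection will be conducted across about 3 to 5 cohorts", and there are three pairs. With five cohorts of two locations, 5 - 3 = 2 cohorts would have to reuse a pair if no other pairing is made, and a late draw is impossible where the arm is already known. There, still withhold the materials until recruitment closes, and have staff approach every family that appears eligible, using the existing common invitation.
- State that the single allergy criterion in section 6.1 is applied identically at all six restaurants.

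The cost is postage for in-person cohorts. Restaurant staff training and the preparation of signs and toys would also have to fit between the last baseline and the start of exposure. The protocol does not say how long that gap is, so a short one may have to be fixed. The 2023 survey cited in section 10.2 suggests that data collection may already have begun; if so, the change can apply only to later cohorts.
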